2.7.3 Aim 3 Analysis: (CR app vs CR+eCBT app)

In regression models above (6-month endpoint or longitudinal), we will include as intervention indicators, CEP vs TA, CR app vs. CR+eCBT app, and their interaction. From estimated models, we will contrast a linear combination of coefficients to estimate CR vs CR+eCBT effects within each CEP or TA group and average effects across these interventions; and conduct stratified analyses by client baseline measures.

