2.4 Measures

2.4.1 Measures for Client/Community Participants

We consider MHRQL (MCS-12) and depression (PHQ-8) as the primary outcomes. We include secondary outcomes as: individual resilience (BRS), physical health quality of life (PCS-12), mental health wellness, social determinants of health, behavioral health hospitalization, work loss days, and general anxiety disorder (GAD-2). Mediating factors are: self-efficacy in coping with depression, social contacts and use of health and social-community and disaster services for these concerns.^{17,18} We will assess sociodemographic factors (age, gender, race/ethnicity, education, insurance coverage, family composition, family income, employment status) as moderators. We also assess exposure to social risk factors, disasters exposure and concern, post-traumatic stress disorder symptoms (PC-PTSD-5), presence of chronic medical conditions, and perceived community efficacy in dealing with disasters.^{19,20} We also have the option of tailoring follow-up measures to specific events (e.g., floods, oil spill).^{21,22} We will explore utilizing open-ended answers to “how are things going now?” to identify linguistic markers of resilience (e.g., emotional positivity).²³ Measures have been formulated with stakeholder and Leadership Council input.

Primary Outcomes

- a) Mental Health Related Quality of Life (MCS-12); SF-12

Changes in mental health-related quality of life defined by a 12-item mental composite score (MCS-12). On a scale of 0-100, 40 is a standard cut-point for poor quality of life.

- b) Depression (PHQ-8)

Depression severity defined by an 8-item Patient Health Questionnaire, scores 0-24. PHQ-8 score of 10 or greater indicates at least moderate depression.

Secondary Outcomes

- c) Brief Resilience Scale (BRS)

Individual resilience is measured on a 1-5 point scale. Scores below 3 indicate low resilience; scores above 4.3 indicate high resilience.

- d) Physical health quality of life (PCS-12); SF-12

Physical functioning using a standardized continuous 12-item physical composite score.

- e) Mental Wellness Indicator

Self-reported indicator of mental wellness; a response of at least "sometimes in the prior 4 weeks" on feeling calm or peaceful, having energy, or being happy.

- f) Social Determinants of Health

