2.6.7 Power calculations

The power calculations were based on expecting a percentage point difference between groups ranging from 8 to 10. With enrolling 600 to 720 individuals per group (1200 to 1440 in total), 80% power was projected to detect the difference between groups ranging from 9.3% to 10.7% with alpha level of 0.05 (two-sided) and ICC=.01, allowed a retention rate of 65-75% at 6 months follow-up.²⁷ For outcome measures assessed monthly during the 6-month period, the proposed sample size with 60% retention is adequate for a between group difference of 7.3-7.9%.

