2.7 Proposed Analysis

2.7.1 General Issues

a) Modeling. We will use an intent-to-treat (ITT) framework and hierarchical approach with information on programs, service providers/staff, and clients. We will conduct bivariate analyses to identify potential covariates for multiple regressions and compare unadjusted and adjusted intervention coefficients to assess confounding. We will explore transformations and two-part models for skewed counts with smearing estimates for retransformation. b) Missing data. For missing data (item or survey non-response) we will use logical imputation for items as

appropriate and hot-deck multiple imputation using a predictive mean-matching method for item non-response.^{29,30} c) Weights. We will create enrollment weights to represent intended populations.^{31,32} d) Multiple Comparisons. We will consider methods that incorporate bounds on probability of false findings of significance, e.g., false discovery rate.³³ e) Multilevel Data: We will apply multi-level (i.e., hierarchical or random coefficient) models to account for clients within programs and three-levels for longitudinal data having repeated measures within clients.²⁷

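### Eight moderators are named, but the plan states only stratified analyses, with no intervention-by-moderator interaction test and no rule for claiming a subgroup difference

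*Combined protocol and SAP*

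**What the plan says.** Section 2.4.1 (Measures for Client/Community Participants) sets the moderator question: "We will assess sociodemographic factors (age, gender, race/ethnicity, education, insurance coverage, family composition, family income, employment status) as moderators".

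The one clause on analysing effects by client baseline characteristics ends section 2.7.3 (Aim 3 Analysis): "conduct stratified analyses by client baseline measures". It gives no strata, cut-points or decision rule. Section 2.7.2 (Aim 2 Analysis) has no such clause.

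Section 2.7.3 does specify one interaction. The model's intervention indicators are "CEP vs TA, CR app vs. CR+eCBT app, and their interaction". This crosses the two randomized interventions with each other and involves no client characteristic.

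On multiplicity, section 2.7.1 says: "We will consider methods that incorporate bounds on probability of false findings of significance, e.g., false discovery rate". It does not tie this to subgroups.

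**The concern.** A moderator question asks whether the intervention effect differs between, say, employed and unemployed clients. That is a question about the difference between two effects. Estimating or testing the effect separately in each stratum does not answer it, because each stratum has about half the data and two results can fall on opposite sides of 0.05 by chance when the true effects are equal.

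As written, the plan poses the question and states no test for it. It also leaves the strata and the standard of evidence open until results are available. The sample is meant to be diverse (section 2.6.1), and the results are to feed community and policy recommendations (section 2.7.7). An unsupported statement that an approach helps one group and not another could carry into those recommendations.

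**Working it through.** **Inputs from section 2.6.7.** Sample size and power: "With enrolling 600 to 720 individuals per group (1200 to 1440 in total), 80% power was projected". The stated detectable range is 9.3-10.7 percentage points, for a two-sided alpha of 0.05, an ICC of 0.01 and 65-75% of clients retained at 6 months. The expected effect is "a percentage point difference between groups ranging from 8 to 10". Section 2.6.2 expects at most 60 programs.

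**Assumptions, because the documents do not give them.** Event rate near 50%, so the variance of a difference is 0.5/n with n per group; 60 programs of equal size; two equal strata per moderator.

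**Step 1: reproduce the plan's figure.** The detectable difference is 2.80 × √(0.5/n_eff), where 2.80 = 1.96 + 0.84, n_eff = n/DE, DE = 1 + (m − 1) × 0.01, and m is retained clients per program.

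- 600 × 0.65 = 390 per group; m = 780/60 = 13; DE = 1.12; n_eff = 348; detectable difference 10.6 points (plan: 10.7).
- 720 × 0.75 = 540 per group; m = 1080/60 = 18; DE = 1.17; n_eff = 462; detectable difference 9.2 points (plan: 9.3).

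The plan's range is reproduced, so the assumptions are a fair working basis.

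**Step 2: power in a half-sample stratum.** Halving n also halves m.

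- 390/2 = 195; m = 6.5; DE = 1.055; n_eff = 185; standard error 5.20 points; detectable difference 14.6 points.
- 540/2 = 270; m = 9; DE = 1.08; n_eff = 250; standard error 4.47 points; detectable difference 12.5 points.

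The app comparison is randomized by individual (section 2.5.2). Without the design effect its standard errors are 5.06 and 4.30 points.

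**Step 3: disagreement when the effect is the same in both strata.** If each stratum has power p, the chance that exactly one is significant is 2p(1 − p).

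| Retained per group | True effect in both strata | p, with design effect | Exactly one significant | p, without design effect | Exactly one significant |
|---|---|---|---|---|---|
| 390 | 8 points | 34% | 45% | 35% | 46% |
| 390 | 10 points | 49% | 50% | 51% | 50% |
| 540 | 8 points | 43% | 49% | 46% | 50% |
| 540 | 10 points | 61% | 48% | 64% | 46% |

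Unequal strata are worse. For an effect that the whole sample detects with 80% power, a 30/70 split gives stratum power of 34% and 65% and disagreement of 55%. A 20/80 split gives 24% and 71%, and 61%.

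**Step 4: no effect anywhere.** For one moderator, the chance of exactly one significant stratum is 2 × 0.05 × 0.95 = 9.5%. For the app comparison, 8 moderators × 2 strata × 2 primary outcomes = 32 tests, and 32 × 0.05 = 1.6 expected false positives. If CEP vs TA were stratified too, there would be 64 tests and 3.2.

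**Step 5: the interaction test.** With two equal strata and a uniform effect, it gives a false claim of effect modification 5% of the time (5.0% in simulation), against 45-50% for comparing stratum significance. Its standard error is twice that of the overall effect. For an interaction as large as a main effect that has 80% power, the standardized value is 2.80/2 = 1.40 and power is about 29%. For the app comparison, the interaction detectable with 80% power is about 17-20 points.

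**The case against.** A reader might infer that the plan has chosen stratification in place of interaction tests, and that subgroup claims will rest on one stratum being significant and another not. The documents support neither. Section 2.7.3 excludes no interaction test and states no inference rule. Stratum estimates with confidence intervals would fit its wording. The 45-50% therefore measures what would happen if results were read that way, which the plan does not say.

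Other objections:

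- **The two clauses are not linked.** Section 2.4.1 lists measures, so assessing the moderators could mean only collecting them, and section 2.7.3 does not call its stratified analyses moderator analyses. This stands as a point about wording. But if the clauses are unrelated, the named moderators have no stated analysis at all. If stratum contrasts are meant to come from the fitted model, that model needs moderator terms that it does not list.
- **The test count.** The stratified clause is in the Aim 3 section only, so 32 tests is the supported count; 64 would assume an Aim 2 analysis that is not stated. Two strata per moderator is also assumed, and race/ethnicity, education and insurance need not be binary.
- **The power scale.** The primary outcomes, MCS-12 and PHQ-8, are scores with cut-points. Section 2.6.7 gives neither the endpoint nor the event rate behind its percentages. The figures follow the plan's own percentage scale and need not carry over to analyses of the scores.
- **Multiplicity.** The false discovery rate is already mentioned, though only for consideration. Interaction tests also need it: 8 moderators × 2 outcomes = 16 tests, or 0.8 expected false positives unadjusted.
- **Importance.** Section 2.1 has no moderator hypothesis, and the main comparisons do not depend on this. That limits the weight of the point.

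**Conclusion.** The point holds as an omission. The plan names eight moderators, states only stratified analyses by client baseline measures, and gives neither an intervention-by-moderator test nor a rule for claiming that effects differ. The CEP-by-app interaction answers a different question.

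The size of the risk rests on event rates near 50%, 60 equal programs and equal halves. On those terms stratum power is about 34-64% at 8-10 points, and a uniform effect would look discordant about 45-50% of the time per moderator. With no effect, about 1.6 false positives are expected from the 32 app-comparison tests. The exact figures would move with other assumptions. The principle would not, since stratum-specific results do not test a difference between strata under any of them.

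This should be corrected. It concerns non-primary analyses and leaves the main Aim 2 and Aim 3 comparisons as they are.

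**What to change.** In section 2.7.3:

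1. Add intervention-by-moderator interaction terms to the multilevel model already planned in section 2.7.1, for the eight factors named in section 2.4.1. Fix their categories in advance and use one joint test where a factor has more than two levels.
2. State that any claim of effect modification rests on those terms, with the false discovery rate applied to that family of tests.
3. Keep the stratum estimates with confidence intervals, beside the interaction estimate, as description only.
4. State which comparison (app, CEP vs TA, or both) and which outcomes are covered, and label the analyses exploratory.

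This changes analysis wording only and needs no new data or larger sample. The real cost is the low interaction power shown in step 5 of the working. Few subgroup differences will be claimed, and a non-significant interaction must not be reported as evidence that effects are equal.

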2.7.4 Qualitative Analysis

We will use several qualitative data collection methods.³⁵ We will use recorded interviews to assess stakeholder priorities (Aim 1), coalition strategies and strengths, and trends in services and disaster response (Aim 4). We will conduct case studies of CEP coalitions to describe coalition development, toolkit modification and training implementation using meeting notes, written plans, interviews, and group discussions at proposed learning collaboratives.³⁶⁻³⁸

2.7.5 Linguistic Predictors

We will explore the feasibility of identifying linguistic predictors of resiliency to inform future research. For this purpose, we will use longitudinally collected, open-ended responses on the monthly brief surveys and use automated text transcription algorithms to extract lexical and vocal acoustic features, associated with hope and stressor response.^{23,39-43,37-40} We will use

supervised learning models (i.e., support vector machine) to explore linguistic features as resilience predictors, i.e., mental wellness and MHRQL.

2.7.6 Mixed-Methods Analyses

For thematic analyses we will enter data into MaxQda software. Academic and community members identify themes coding 5-10 percent together and resolving discrepancies by consensus.^{44,45} We will code data deductively based on study goals, e.g., training plans, and inductively based on emergent themes, e.g., new priorities.⁴³ We will conduct comparative analyses to identify themes across coalitions and triangulate results to describe context, strategies to address resilience, implementation strategies and outcomes. All analyses will be partnered with stakeholders.⁴⁴

2.7.7 Partnered Synthesis

We will use all sources of data in community conferences to support academic and community partners in generating research, community improvement and policy recommendations, following the model of CPPR that we have applied in Louisiana and Los Angeles.^{12,24,45}

3. Data Safety Plan

3.1 Responsibility for Data Safeguarding

The principal investigator, [name], MPH has the ultimate responsibility for data safeguarding.

All project staff will have completed the CITI IRB training and LSUHSC-NO KDL training (LSUHSC-NO personnel) or other HIPAA and institutional-specific training (non-LSUHSC-NO personnel), and will abide by applicable compliance documents in accord with university policies and procedures to protect the privacy of the research data for their entire tenure on this project.

3.2 Data Storage

Data used as part of this study will be stored primarily on a server located at the Center for Health Services and Society at UCLA. The server is located in a locked server room and cabinet. The Center IT administrators will perform regular and encrypted backups of the data. The server is protected using standard security practices including being located behind the UCLA firewall, accessible only by designated users from our staff located at UCLA or connected through the UCLA Mednet VPN from an offsite location. Data transferred using devices (such as USB drives and laptops) will be encrypted following UCLA Health device encryption policies. Storage and access procedures are in full compliance with UCLA Health data security policies.

3.3 Participant Compensation Information

LSUHSC policy requires the collection of participant social security numbers (SSN) in order to receive payment for study participation. At the time of consent, New Orleans recruitment staff

will enter participant SSN, first and last name, address, date of screening, and payment dollar amount into the ClinCard system using study-specific iPads connected to the internet using a Wifi hotspot. ClinCards are a secure, LSUHSC-NO approved method of compensating study participants that function as loadable debit cards. In the event the Wifi hotspot isn't working, a tracking sheet will be filled out by IRB-approved study staff to record ClinCard token numbers, amounts, the participant's full name, SSN, and mailing address. These will only be recorded on paper and will be destroyed immediately after input into the ClinCard system. The participant's information will be used only for payment purposes, and never for research. All research and payment information will be stored separately.

3.4 Data Transmittal

The default mechanism for transferring files electronically includes encrypting files (256-bit AES approved using software that supports .zip format, e.g. WinZip) into a single archive, in compliance with UCLA Health data security policies. That archive may be delivered electronically (e.g. an e-mail attachment) or on removable media. In addition, direct connections between computers using encrypted communication protocols such as SSH and SFTP may also be employed.

3.5 Online Screening and Consent

The electronic screening and consent will be delivered via a website created using the Chorus platform. In the event electronic screening and consent are technologically infeasible temporarily, hard copy paper screening and consent will be substituted. Paper copies' data will be then entered as soon as feasible into the online system and paper copies will be shredded. Chorus is a web application that allows individuals to create websites and mobile apps to collect and display data similar to sites such as SurveyGizmo. Chorus was created at the Center for Health Services and Society at UCLA and is hosted by a server at that center. It has been approved by the UCLA Office of Information Security for use in research projects as well as patient care including protected health information. All communication to and from the server is encrypted using SSL certificates. It is also used by multiple IRB-approved studies at UCLA. Study staff will be able to export data in comma-separated format (CSV) and will import that to the study server for analysis.

3.6 Audit and Monitoring Plans

We have no specific auditing or monitoring plans.

3.7 Data Safeguarding Procedures

Our standard data safeguarding procedures include the following:

Additional electronic files used by study staff will be stored on secured, password protected computers accessible only to study staff members. At UCLA, the network is set up as a Windows domain and all files will be stored on a secured Window file server with folder-level password protection to ensure that only study staff have access to study files.

All study staff will also abide by basic procedures for protecting identifiable private and proprietary data that have been adopted by the project as a whole. For each stage of the research process, the following procedures will be implemented:

Training staff on data sensitivity and data safeguards being employed.

Processing sensitive data in a centralized location with established access control procedures.

- Storing sensitive hardcopy in locked files when not in use.
- Restricting access to shared disk files through appropriate use of file permissions.
- Printing sensitive material only when absolutely necessary. When it is necessary, project staff will ensure that an authorized person is at the printer when the sensitive material appears.
- Using Certified mail, return receipt requested, for sensitive data and Registered mail for very sensitive data when transferring materials by mail. (No transfer by mail is planned, but this procedure would be followed if applicable.)
- Re-training staff and reviewing sensitive data inventory and data safeguards annually.
- Reporting all serious violations of the Data Safeguarding Plan in writing to the Principal Investigator, with a copy to the Office of Research Services.

References

